Effect of rasagiline on balance in Parkinson's disease as measured by computerized posturography

[name]

Approved: 9/15/2014

Department of Neurology

New York Medical College, Valhalla, NY

United States of America

Corresponding Author

[name]

[name]

[name]

United States of America

[contact]

[contact]

Email: [contact]

Keywords: rasagiline, balance, posturography, Parkinson's disease

Abstract:**Background:**

Falls occur in a majority of Parkinson's disease (PD) patients. Balance disturbance can be measured by computer dynamic posturography. The effect of monoamine oxidase inhibition on PD patients as measured by computer dynamic posturography has not been previously studies.

Methods:

The study will test the hypothesis that therapy with rasagiline improves balance in PD patients as measured by computerized dynamic posturography. 5 subjects will be randomized to rasagiline or placebo and 5 further subjects will be randomized to rasagiline as adjuvant therapy versus placebo. Subjects will be analyzed by computerized dynamic posturography testing. The device measures body sway under varying visual and vestibular cues and is used for assessment of balance. Subjects will be evaluated at baseline prior to taking first tablet as well as at 4 weeks and 8 weeks. In the adjuvant therapy arm, subjects will be evaluated on rasagiline but in a functional OFF state for their other PD medications. If the scores are normally distributed, we will determine whether data variance is approximately equal in all tested groups. If these conditions are met, data evaluation will continue using repeated measures ANOVA with between factor of drug (levels: rasagiline, placebo) and within factor of treatment (levels: before, after). Level of significance will be preset to 0.05.

Background:

Posturography testing for Parkinson's disease patients on monoamine oxidase (MAO) inhibitors in general has not been studied previously. In Wood's study of patients with Parkinson's disease, falls occurred in 68.3% of the subjects [1]. In Ebmeier's population study of idiopathic Parkinson's disease patients, signs of postural instability on clinical examination were among the factors listed in premature death [2].

Hypothesis

The hypothesis is that therapy with rasagiline improves balance in PD patients as measured by computerized dynamic posturography.

Methods:**Inclusion Criteria:**

1. 18 years old or above

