2. Clinical diagnosis of Parkinson disease by verified by movement disorders expert at the initial study visit with at least two cardinal signs of the disease (rest tremor, bradykinesia, rigidity, and postural instability).
3. For the monotherapy arm, patients must not be on amantadine, dopamine agonists, or levodopa. For the adjuvant therapy arm: Patients must be on a stable dose of their current medication for treatment of Parkinson disease which may include any combination of the following: amantadine, trihexiphenydil, dopamine agonist, and/or levodopa.
4. Patients may continue their stable dose of tricyclic, selective serotonin reuptake inhibitor, or serotonin norepinephrine reuptake inhibitor if they are on these medications at randomization.

Exclusion Criteria:

1. Catechol-O-Methyltransferase (COMT) inhibitor therapy use 30 days prior to start of study (both study arms).
2. Dopamine receptor blocker use (such as quetiapine) one week prior to taking study drug
3. For both monotherapy and adjuvant therapy arms: use of MAO inhibitor therapy including selegiline or rasagiline within 30 days prior to taking study drug and first posturography evaluation.

Study Visits:**Screening:**

Patients will be evaluated by movement disorders expert who will confirm diagnosis of Parkinson disease as stipulated in inclusion criteria. Blood pressure and heart rate, as well as a complete Unified Parkinson Disease Rating Scale (UPDRS) evaluation will be performed.

Randomization:

Subjects will be randomized by facility pharmacy to either placebo or rasagiline 1 mg daily for 8 weeks. There will be 5 rasagiline monotherapy and 5 matching placebo subjects as well as 5 rasagiline adjuvant therapy and 5 matching placebo subjects.

Computerized dynamic posturography evaluation:

Subjects will be evaluated at baseline prior to taking first tablet as well as at 4 weeks and 8 weeks. In the adjuvant therapy arm, subjects will be evaluated on rasagiline but in a functional OFF state for their other PD medications.

Functional OFF will be defined as at least 24 hours post last dose of long acting dopamine agonist or levodopa extended or continuous release formulations, at least 8 hours post last dose of immediate release dopamine agonist, immediate release levodopa, or trihexyphenidyl.

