Subjects will undergo computerized dynamic posturography testing via apparatus manufactured by Neurocom, Inc. This device is clinically used for measurement of balance impairment. It measures body sway under varying visual and vestibular cues [3]. Motor control test (MCT) measuring body sway during small translations of the support surface will also be used.

Conclusion of study:

Subjects will stop taking rasagiline or placebo once their 8 week supply runs out.

Power analysis to determine the number of subjects

To estimate number of subjects needed for the posturography test, we performed a power analysis using the software G*power [4]. For inputs, data from the effect of dopamine depleter tetrabenazine on posturography in Huntington's disease was used [5].

The strategy composite score here during the tetrabenazine ON state was 79.2, during tetrabenazine OFF state it was 63.5. Averaged SD for these two outcomes was 11.5 and the total sample size was 10. These data were used to calculate the anticipated effect size. This input provided the Effect Size $f = 0.6826087$ (Table 1).

Input of the effect size value into the G*power with requested $\alpha=0.05$ and power $(1-\beta)=0.9$, weighing in the repeated measurements (before and after rasagiline) with very low correlation among repeated measures resulted in returned total sample size of 10 subjects Table 1 (please see the table of calculated inputs and outputs below). This total number will be randomized into 2 groups of subjects: rasagiline monotherapy and placebo study arm. Similarly, there will be 10 subjects in the study arm with rasagiline as an adjuvant therapy versus placebo.

F tests - ANOVA: Repeated measures, between factors

Analysis: A priori: Compute required sample size

Input:	Effect size f	=	0.6826087
	α err prob	=	0.05
	Power ($1-\beta$ err prob)	=	0.9
	Number of groups	=	2
	Repetitions	=	4
	Corr among rep measures	=	.1
Output:	Noncentrality parameter λ	=	14.337066
	Critical F	=	5.317655
	Numerator df	=	1.000000
	Denominator df	=	8.000000
	Total sample size	=	10
	Actual power	=	0.910691

Table 1. G*power software inputs and outputs for statistical power

General approach for statistical evaluation of the study data

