The output of the posturography testing are computer-calculated scores. Though these scores are discrete (do not represent a continuous variable), they still may fit the requirements of parametric statistical tests. Thus, we will first test the raw scores for normal distribution using a Kolmogorov-Smirnov test versus dataset with known Gaussian distribution. If the scores are normally distributed, we will determine whether data variance is approximately equal in all tested groups. If these conditions are met, we will continue data evaluation using repeated measures ANOVA with between factor of drug (levels: rasagiline, placebo) and within factor of treatment (levels: before, after). Level of significance will be preset to 0.05. Since no multiple comparisons are planned, there will be no adjustments of p.

If we do not find the Gaussian distribution of scores or if the variances among the groups are unequal (difference of one order of magnitude or more), we will calculate non-parametric statistics to determine differences. For this purpose we will use Wilcoxon Signed Rank test and evaluate separately rasagiline and placebo groups with p preset to 0.05.

Abbreviations

COMT: Catechol-O-Methyltransferase

HD: Huntington's disease

MCT: Motor control test

PD: Parkinson's disease

References:

1. Wood BH, Bilclough, Bowron A. Incidence and prediction of falls in Parkinson's disease: a prospective multidisciplinary study. *J Neurol Neurosurg Psychiatry* 2002;72:721-725
5. [name], Davidson, A., Ondo, W.G., and Cohen, H.S. Effect of tetrabenazine on computerized dynamic posturography in Huntington disease patients. *Parkinsonism and Related Disorders* 2012;18(7):896-8.

Declarations**Ethics Approval and Consent to Participate**

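### The plan does not say whether the two cohorts are tested once or separately, its stated power of 0.911 belongs to a different test, and its fallback never compares drug with placebo

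*Combined protocol and SAP*

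**What the plan says.** The Hypothesis section states a single hypothesis: "The hypothesis is that therapy with rasagiline improves balance in PD patients as measured by computerized dynamic posturography".

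The Randomization section describes two non-overlapping cohorts: "There will be 5 rasagiline monotherapy and 5 matching placebo subjects as well as 5 rasagiline adjuvant therapy and 5 matching placebo subjects". Eligibility differs between them, and only the adjuvant cohort is assessed in a functional OFF state.

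The power section contains one calculation (Table 1): between-factors repeated measures ANOVA, f = 0.6826087, alpha 0.05, 2 groups, 4 repetitions, correlation 0.1. It returns N = 10, denominator df 8 and power 0.910691. The number is given to monotherapy: "This total number will be randomized into 2 groups of subjects: rasagiline monotherapy and placebo study arm". It is then carried over without a second calculation: "Similarly, there will be 10 subjects in the study arm with rasagiline as an adjuvant therapy versus placebo".

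The analysis section (General approach for statistical evaluation of the study data) names one model: "repeated measures ANOVA with between factor of drug (levels: rasagiline, placebo) and within factor of treatment (levels: before, after". It sets significance at 0.05 and adds: "Since no multiple comparisons are planned, there will be no adjustments of p". If normality or equal variance fails: "For this purpose we will use Wilcoxon Signed Rank test and evaluate separately rasagiline and placebo groups with p preset to 0.05".

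Three assessments are scheduled: "Subjects will be evaluated at baseline prior to taking first tablet as well as at 4 weeks and 8 weeks". The analysis section does not say which of the two later visits is the after level.

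**The concern.** The sizing points to two comparisons, one per cohort. The analysis section describes one model and says there is no multiplicity. Nothing says whether the ANOVA is run once on 20 subjects or twice on 10, or, if twice, whether one or both cohorts must succeed. A reader therefore cannot tell which test decides the hypothesis or what its error rate is.

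Two further problems do not depend on that question. The test in Table 1 is not the test in the analysis section, so the stated power may not apply on either reading. And the fallback looks at rasagiline and placebo one group at a time, so it cannot answer a question about drug against placebo.

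**Working it through.** **1. Reproduce Table 1.** Inputs from the power section: means 79.2 and 63.5 (difference 15.7), SD 11.5, correlation 0.1, 4 repetitions, N = 10.
- f = (15.7 / 11.5) / 2 = 0.6826.
- λ = f² × N × m / (1 + (m − 1)ρ) = 0.6826² × 10 × 4 / 1.3 = 14.337.
- Critical F(1, 8) = 5.318; power = 0.9107.

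The stated figures reproduce exactly. The arithmetic is not at fault.

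**2. Same formula, two levels.** The planned ANOVA has before and after only. With m = 2: λ = 0.6826² × 10 × 2 / 1.1 = 8.472, power 0.723. Even this assumes that the full group difference is already present at baseline, because the main effect averages over both levels.

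**3. The drug effect in the planned model.** A drug effect on change is the drug by before/after interaction, which is equivalent to comparing mean change between groups. I take no group difference at baseline and the plan's 15.7 at the after visit.
- SD of change = 11.5 × √(2 × 0.9) = 15.43.
- One cohort of 10: λ = (15.7 / 15.43)² × 10 / 4 = 2.589, df 1 and 8, power 0.295.
- All 20: λ = 5.177, df 1 and 18, power 0.577. Adding a cohort term (df 17) leaves it at 0.574.

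| Test | N | Power |
|---|---|---|
| Table 1: main effect, 4 repetitions | 10 | 0.911 |
| Main effect, 2 repetitions | 10 | 0.723 |
| Drug by before/after, one cohort | 10 | 0.295 |
| Drug by before/after, pooled | 20 | 0.577 |
| Table 1 formula applied to all 20 (df 18) | 20 | 0.999 |

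The fall from 0.911 to 0.295 occurs at a fixed N of 10. It comes from the number of repetitions and the type of effect, not from how the cohorts are handled.

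**4. Error rate if the cohorts are tested separately.** The subjects are disjoint, so the tests are taken as independent.
- Either cohort counts: 1 − 0.95² = 9.75% two-sided; in the improvement direction 1 − 0.975² = 4.9%, against 2.5% for one test.
- Both must succeed: no inflation.

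**5. Fallback.** A signed-rank test within the rasagiline group and another within the placebo group give two within-group p values and no contrast between them. If also split by cohort (n = 5), the smallest exact two-sided p is 2 / 2⁵ = 0.0625, so 0.05 cannot be reached. A rank-sum test of 5 against 5 has 252 allocations, so its smallest two-sided p is 2 / 252 = 0.008.

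**6. One pooled option, for scale.** Simulated ANCOVA of all 20 subjects with cohort and baseline, on the plan's inputs:
- Week 8, equal effects: power about 0.80; 0.25 if one cohort has no effect.
- Mean of weeks 4 and 8: 0.96 if the full effect is present by week 4, about 0.81 with half of it, about 0.47 with none.
- At a correlation of 0.1, the gain over 0.58 comes from no longer subtracting a nearly unrelated baseline. A week-8 comparison with cohort but no baseline term gives 0.82.

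**The case against.** The strongest reply is that the plan is less ambiguous than it looks. Separate eligibility, separate allocation, a different test condition and the sizing text all suggest one test per cohort, and on that reading N = 10, alpha 0.05 and df 8 fit each comparison. Different patients in different treatment settings may reasonably be two questions, each at 0.05 without adjustment. Much of this stands. It means that adjustment is not shown to be required. It does not rescue the stated reason, because the plan has one hypothesis and says that no multiple comparisons exist, while this reading has two.

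A reader might infer that the trial's error rate is 9.75%, or 4.9% for improvement. The documents do not support that: both figures need a rule that success in either cohort is enough, and the plan states no success rule.

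A reader might also infer that the low power follows from the cohort or multiplicity problem. It does not. On the pooled reading the plan's own formula gives 0.999, so the cohort mismatch by itself would not make the trial look too small.

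Finally, pooling is not plainly what the plan intended. It averages two populations that the power section sizes one at a time, and nothing in the documents favours the mean of weeks 4 and 8. Pooled ANCOVA is one option, not the necessary correction.

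The declarations say that no patients were enrolled and no data were gathered, so no result is affected. The point matters to anyone who takes up this plan.

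**Conclusion.** The concern holds with these limits. Three things need changing.

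- **Power.** The stated 0.911 is not the power of the planned test on either reading. On the plan's difference, SD and correlation, with the full effect at the after visit, it is about 0.29 in one cohort and 0.58 in all 20, against a requested 0.90. These figures depend on the correlation: at an assumed 0.5 the pooled before/after test reaches about 0.82.
- **Fallback.** It never compares drug with placebo, and if split by cohort it cannot reach two-sided 0.05.
- **Number of tests.** The sizing and the analysis do not match. Run per cohort, the reason for leaving p unadjusted is inaccurate. Run once, that reason is sound, but Table 1 sizes another test and the model leaves out the cohort within which subjects are randomised.

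Inflation to 4.9% in the improvement direction is conditional on an either-cohort rule and is not established.

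**What to change.** 1. **Fallback.** Replace the two signed-rank tests with one rasagiline versus placebo rank-sum test on change or baseline-adjusted score, stratified by cohort if the cohorts are pooled.
2. **Power.** Replace Table 1 with the power of the test actually planned, with the number of repetitions and the type of effect matching the ANOVA, and say which visit is the after level.
3. **Number of tests.** State whether the ANOVA is run once or per cohort, and make the no-adjustment sentence agree.
   - If pooled: add cohort as a factor and give a single primary test as the reason for not adjusting.
   - If separate: state the success rule, and either adjust or declare two distinct claims, each at 0.05.

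One pooled option is a week-8 ANCOVA with cohort and baseline on the strategy composite score, the score used for sizing. Its power is about 0.80 with equal effects, still below the requested 0.90, and 0.25 if one cohort has none. It averages two populations and makes cohort results secondary. Using the mean of weeks 4 and 8 raises power to 0.96 only if the effect is complete by week 4.

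The text changes need no new visits or measurements. The real cost is that an honest power statement may show 10 per cohort to be too few. If two separate claims are kept, the sample size would have to be redone.

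### The tenfold-variance and normality checks can replace the rasagiline-placebo ANOVA with separate within-arm signed-rank tests, which contain no comparison with placebo

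*Combined protocol and SAP*

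**What the plan says.** The combined protocol and SAP sets out a chain of decisions under the heading on the general approach for statistical evaluation.

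- **Normality.** It begins: "we will first test the raw scores for normal distribution using a Kolmogorov-Smirnov test versus dataset with known Gaussian distribution". The version of the Kolmogorov-Smirnov test is not given.
- **Variance.** If the scores pass, "we will determine whether data variance is approximately equal in all tested groups". The tested groups are not defined.
- **Main analysis.** If both conditions hold, the analysis is a repeated-measures ANOVA with drug as the between factor and a "within factor of treatment (levels: before, after". The effect to be tested (drug, time or their interaction) is not named.
- **Fallback.** If normality is not found, or "if the variances among the groups are unequal (difference of one order of magnitude or more", the plan is: "we will use Wilcoxon Signed Rank test and evaluate separately rasagiline and placebo groups with p preset to 0.05".

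The Hypothesis section states the aim: "The hypothesis is that therapy with rasagiline improves balance in PD patients as measured by computerized dynamic posturography". The Randomization section gives the sizes: "There will be 5 rasagiline monotherapy and 5 matching placebo subjects as well as 5 rasagiline adjuvant therapy and 5 matching placebo subjects". The power section sizes each cohort separately at 10 subjects. Of the monotherapy cohort it says: "This total number will be randomized into 2 groups of subjects: rasagiline monotherapy and placebo study arm".

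**The concern.** The trial randomises against placebo so that the effect of rasagiline can be separated from practice on the platform, placebo response and other changes over 8 weeks. The ANOVA can make that separation. Two signed-rank tests, one per arm, cannot: each asks only whether scores moved within that arm. A significant result on rasagiline beside a non-significant one on placebo is not a test of the difference.

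The rule that chooses between these analyses relies on sample variances with 4 degrees of freedom each. At that size a tenfold ratio can arise from sampling noise alone, so the randomised comparison can be dropped when nothing is wrong with the data. What follows depends on how the signed-rank test is run, which the plan does not say. Either the diverted cohort cannot reach significance, or it can, but on a test that a shared change can trigger. These are alternatives and do not add up.

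**Working it through.** **Inputs.** From the documents: 5 per arm in each cohort; tenfold variance trigger; alpha 0.05; means 79.2 and 63.5 and SD 11.5 from the power section; correlation 0.1 from Table 1. Assumed: normal scores, equal true variances, correlations of 0.5 and 0.9 as a range, and 15.7 as the drug difference in change.

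**1. The plan's own figure.** f = (79.2 − 63.5)/(2 × 11.5) = 0.6826. With N = 10, 4 repetitions and correlation 0.1, λ = 0.6826² × 10 × 4/(1 + 3 × 0.1) = 14.337. Against F(1, 8) with critical value 5.318, power is 0.911. Table 1 reproduces. It is headed as a between-factors test, so this is not the power of the drug-by-treatment interaction used in step 4.

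**2. How often the tenfold rule fires when true variances are equal.** For two arms with one variance each, the chance is exact: 2 × P(F(4,4) ≥ 10) = 2 × 0.0233 = 0.0466. The chance that at least one of two cohorts switches is 1 − (1 − 0.0466)² = 0.091. Most other readings come from simulation (400,000 cohorts, largest over smallest variance at least 10):

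| Variances compared | Correlation 0.1 | 0.5 | 0.9 |
|---|---|---|---|
| Two arms, one variance each | 4.7% | 4.7% | 4.7% |
| Two arms, at either visit | 9.1% | 9.0% | 7.9% |
| Four drug × before/after cells | 17% | 15% | 10% |
| Before and after scores pooled within arm | 0.2% | 0.4% | 2.3% |
| Cohorts pooled to 10 per drug | 1% or less | 1% or less | 1% or less |

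**3. What the fallback can show with 5 subjects.** The most extreme outcome is all five changes in one direction.
- Exact, two-sided: 2/2⁵ = 0.0625.
- Exact, one-sided: 1/2⁵ = 0.031.
- Normal approximation: the rank sum is 15, its mean 7.5 and its SD √(5 × 6 × 11/24) = 3.708. Then z = 7.5/3.708 = 2.02 and p = 0.043. With continuity correction, z = 7.0/3.708 = 1.89 and p = 0.059.

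The exact two-sided and continuity-corrected tests can never reach 0.05. The one-sided exact test and the uncorrected approximation can.

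**4. Power with the exact two-sided fallback.** At correlation 0.1 the SD of change is 11.5 × √(2 × 0.9) = 15.43, the standard error of the difference is 15.43 × √(2/5) = 9.76, and the noncentrality is 15.7/9.76 = 1.61. The t-test on change with 8 df, which equals the interaction test, has power 29.5%. Diverted cohorts count as failures. The two-arm rule here compares the variances of each subject's mean score.

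| | Correlation 0.1 | 0.5 | 0.9 |
|---|---|---|---|
| Interaction test, no switch | 29.5% | 47.7% | 98.7% |
| With switch, two arms | 28.1% | 45.5% | 94.1% |
| With switch, four cells | 24.6% | 40.9% | 89.2% |

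Type I error stays below 5% in this case (4.2% to 4.8%).

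**5. Shared change with the uncorrected approximation.** Assume no drug effect and a before-after change of 7.85 (half of 15.7) in both arms; no document supplies this value. At correlation 0.1, if the rasagiline arm is read alone, false positives are 5.5% (two arms) or 7.1% (four cells) over all cohorts. Among four-cell diverted cohorts the rate is about 17%. If placebo must also be non-significant, the overall figures are 5.4% and 6.7%. With no shared change they are 5.0% and 5.3%.

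**The case against.** The strongest reply is that the practical effect is small. The fallback sentence itself names the groups as rasagiline and placebo, so the two-arm reading is natural. On it the rule fires in 4.7% of cohorts and, at the only documented correlation, costs 1.4 points of power (29.5 − 28.1). That stands. The larger figures need the four-cell reading, and the largest also need an assumed correlation of 0.9. On two pooled readings the chance trigger nearly vanishes.

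The hypothesis is also directional and the plan does not state sidedness. With a one-sided exact fallback, power at correlation 0.1 is 30.0% (two arms) or 31.9% (four cells), so none is lost. That stands too: a diverted cohort is lost for certain only under the exact two-sided or continuity-corrected test. The one-sided version remains open to a shared change.

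Three stronger readings are not supported:
- A reader might infer that the switch substantially inflates false positives. That needs a test version that can reach 0.05, a sizeable shared change and, for the higher figures, disregard of placebo, although the plan evaluates both arms.
- A reader might infer that the normality check diverts a large share of cohorts. The wording points to a comparison with a Gaussian dataset or a specified Gaussian distribution. A two-sample test against five Gaussian values rejects only 1% to 2% of the time even with exponential or lognormal scores. The check is a second route to the same fallback, but its frequency cannot be fixed from the text.
- Nothing here shows that missed non-normality invalidates the ANOVA.

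None of this supplies the missing between-arm test in the fallback.

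**Conclusion.** The concern holds as a structural defect of modest average size. Whenever the fallback is used, for good reason or by chance, the plan has no test of rasagiline against placebo, and under an exact two-sided test the cohort cannot reach 0.05. This needs no simulation.

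The frequency and cost do rest on assumptions: normal scores, equal true variances and a chosen meaning of the tested groups. Chance diversion is 4.7% for two arms, about 17/15/10% for four cells at correlations 0.1/0.5/0.9 (only 0.1 is documented), and about 2% or less if scores are pooled within arm or cohorts are pooled. At correlation 0.1 the power cost is about 1 to 5 points from a base of about 29%. That base belongs to the interaction test under an assumed difference in change of 15.7. It should not be set against the 91% in Table 1 as though the switch explained the gap.

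A reader might also suppose that the interaction is already the planned test. The plan lists the two factors but does not name the effect, so choosing it is a decision that has to be written down.

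**What to change.** Stop using the normality and variance checks as decision rules. Prespecify one between-arm test per cohort, for example: *In each cohort the primary test is the drug-by-treatment interaction of the repeated-measures ANOVA (equivalently, the difference between arms in before-after change), two-sided at 0.05, whatever the distribution and variance checks show.*

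Keep residual plots, and a between-arm rank-sum or re-randomisation test on change as a sensitivity analysis. If a non-parametric fallback is retained, it should be one of those between-arm tests, and the tested groups and visits in the variance check should be defined.

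Costs:
- If true variances differ tenfold, the unconditional equal-variance test has type I error of about 6.8% at 5 per arm.
- A re-randomisation p-value is discrete (minimum two-sided 2/252 = 0.008) and costs about 0.3 to 2 points of power.
- As the primary test, the exact rank-sum has less power: 21.6% at correlation 0.1, against 29.9% for the interaction test in the same run.

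The change is wording and a short script, with no effect on design or sample size. The Data Availability section says no data were gathered, so it can be made before any result is seen. It matters only if the protocol is run.

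### The non-parametric fallback never compares rasagiline with placebo, and as an exact two-sided test on 5 subjects per group it cannot reach 0.05

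*Combined protocol and SAP*

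**What the plan says.** The Hypothesis section reads: "The hypothesis is that therapy with rasagiline improves balance in PD patients as measured by computerized dynamic posturography". The Randomization section gives the layout: "There will be 5 rasagiline monotherapy and 5 matching placebo subjects as well as 5 rasagiline adjuvant therapy and 5 matching placebo subjects". The power section sizes the monotherapy stratum as its own two-group comparison of 10, then does the same for the other stratum: "Similarly, there will be 10 subjects in the study arm with rasagiline as an adjuvant therapy versus placebo".

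The section on the general approach to statistical evaluation sets out two routes. If the scores pass checks of normality and equal variance, the analysis is a "repeated measures ANOVA with between factor of drug (levels: rasagiline, placebo) and within factor of treatment (levels: before, after)". If the scores are not Gaussian, or "if the variances among the groups are unequal (difference of one order of magnitude or more), we will calculate non-parametric statistics to determine differences", the plan continues: "For this purpose we will use Wilcoxon Signed Rank test and evaluate separately rasagiline and placebo groups with p preset to 0.05".

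The plan does not say whether the signed-rank test is one- or two-sided, whether its p value is exact or approximate, or whether the strata are pooled.

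**The concern.** The two routes answer different questions. The ANOVA has a between-subject drug factor and so uses the randomisation. The fallback asks, in each drug group alone, whether scores changed from before to after. A significant change on rasagiline with a non-significant one on placebo is not a test of the difference between them. A gain shared by both groups, for example placebo response or practice over repeated posturography, can produce that pattern with no drug effect.

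The group size adds a second difficulty. With five pairs, the signed-rank test has only 32 equally likely sign patterns under the null, so its exact p values are coarse. The trial could enter a route on which no outcome can meet its own significance level.

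**Working it through.** **Inputs.** Group size 5 per drug group per stratum, or 10 if strata are pooled (Randomization). Significance level 0.05 (general approach section). Means 79.2 and 63.5, SD 11.5, correlation 0.1, four repetitions (power section and Table 1). Two-sided testing is assumed. Correlations of 0.5 and 0.7 and any gain common to both groups are also assumptions; the documents give only 0.1.

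**The plan's own figure.** f = (79.2 − 63.5)/11.5/2 = 0.6826. λ = f²·N·m/(1 + (m − 1)ρ) = 0.46595 × 10 × 4/1.3 = 14.337. With critical F 5.3177 on 1 and 8 df, power is 0.9107. Table 1 is reproduced. That power belongs to the between-group ANOVA; the plan gives none for the fallback.

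**Smallest attainable signed-rank p, all subjects changing in the same direction**

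| Version | Calculation | p |
|---|---|---|
| n = 5, exact two-sided | 2/2^5 | 0.0625 |
| n = 5, exact one-sided | 1/2^5 | 0.031 |
| n = 5, normal approximation | z = (15 − 7.5)/√13.75 = 2.02 | 0.043 |
| n = 5, with continuity correction | z = (15 − 7.5 − 0.5)/√13.75 = 1.89 | 0.059 |
| n = 10 (pooled), exact two-sided | 2/2^10 | 0.002 |

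The uncorrected approximation rejects only when all five changes agree in sign, so its true size is 2/32 = 6.25%. One dropout or one zero change raises the exact two-sided minimum to 2/2^4 = 0.125.

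**Chance of entering the fallback through the variance rule** (normal data, equal true variances, ratio of 10 or more)

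- Two groups of 5: 2·P(F(4,4) > 10) = 0.0466.
- Two groups of 10: 2·P(F(9,9) > 10) = 0.0021.
- Largest against smallest of four before/after cells of 5: 0.170, 0.149 and 0.129 at ρ = 0.1, 0.5 and 0.7.

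**Illustration: no drug effect, same gain in both groups.** Simulation of 200,000 trials with 10 per group, normal data, exact two-sided tests and SD of change = √(2(1 − ρ)) SD. Entries are the proportion of trials significant on rasagiline but not on placebo.

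| Common gain (SD) | ρ = 0.1 | ρ = 0.5 | ρ = 0.7 |
|---|---|---|---|
| 0 | 0.046 | 0.048 | 0.046 |
| 0.25 | 0.074 | 0.094 | 0.126 |
| 0.5 | 0.147 | 0.204 | 0.246 |
| 0.75 | 0.223 | 0.248 | 0.185 |
| 1.0 | 0.248 | 0.170 | 0.056 |

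A rank-sum test on change rejects in 0.042 to 0.044 of the same trials. A separate run at ρ = 0.1 agrees: 4.7% at no gain and 25% at a common gain of 10 points (10/11.5 = 0.87 SD).

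**At the plan's own effect**, 15.7/11.5 = 1.37 SD with no placebo change:

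| Quantity | ρ = 0.1 | ρ = 0.5 | ρ = 0.7 |
|---|---|---|---|
| All five rasagiline subjects improve | 0.433 | 0.635 | 0.819 |
| Exact two-sided signed-rank, n = 5, rejects | 0 | 0 | 0 |
| Rank-sum on change, 5 v 5, power | 0.213 | 0.363 | 0.561 |
| Rank-sum on change, 10 v 10, power | 0.527 | 0.781 | 0.943 |

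The 5 v 5 rank-sum test has a minimum p of 2/C(10,5) = 2/252 = 0.0079 and a true size of 0.032. It can reach 0.05, and it compares the groups.

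**The case against.** The strongest reply is that this is a side branch. The main analysis does compare drug with placebo. The variance rule opens the branch by chance in 4.7% of 5 v 5 comparisons and 0.2% of 10 v 10. The 13% to 17% figure needs the before/after cells to count as groups, although the plan calls before/after a within factor. The normality check may seldom open it either. A one-sample Kolmogorov-Smirnov test with estimated mean and SD and standard critical values rejected no samples at n = 5, even from exponential or lognormal data, and at most 2.7% at n = 10. That is only indicative, because the plan's version of the test is unclear. All this limits how often the defect would bite. It does not make the branch valid once entered.

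The n = 5 limit needs exact, two-sided and per-stratum use, and the hypothesis is directional. This stands, so the point is secondary and conditional.

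The two harms rest on different readings: with exact two-sided tests at n = 5 there are no rejections, true or false, while the false-pattern rates assume pooling to 10. The simulation also uses equal-variance normal data that would mostly go to the ANOVA, and scores a decision rule that the plan does not state. This too is fair, and the rates are illustrative only. The missing comparison does not depend on them.

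Finally, the replacement is imperfect. With a true tenfold variance ratio, the exact rank-sum test has size 6.2% at 10 v 10 (4.7% at 5 v 5). The plan also does not say which visit counts as after. The first is a modest inflation; the second needs one added phrase.

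**Conclusion.** The concern holds. As written, the fallback replaces a randomised comparison with two separate within-group tests, so a trial that enters it cannot test its hypothesis. This follows from the wording alone, whatever the sidedness, p-value method or pooling.

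Conditionally on exact, two-sided, per-stratum use, the minimum p is 0.0625 and rejection is impossible at any effect size. In versions that can reject, an assumed common gain of 0.25 to 1.0 SD gives the misleading rasagiline-only pattern in about 6% to 25% of trials with 10 per group, against about 5% with no gain.

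The branch may be entered rarely, but it is the plan's only specified alternative, and its trigger can fire by chance. The declarations say that no data were gathered, so no result is affected and the sentence can be corrected before the protocol is used. It must be corrected before then.

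**What to change.** Replace the fallback sentence with wording such as:

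> If these conditions are not met, rasagiline and placebo will be compared on change from baseline to [named visit, the same as in the ANOVA] with a two-sided exact Wilcoxon rank-sum (Mann-Whitney) or permutation test at 0.05. If all 20 subjects are analysed together, the test will be stratified by monotherapy or adjuvant arm. Within-group signed-rank tests are descriptive only.

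The plan must also state whether the test is run per stratum or on all 20 subjects, and which post-baseline visit is used, since the before/after factor does not choose between weeks 4 and 8.

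The cost is a short wording change, with no added subjects, visits or data. A per-stratum result should be reported with its limit: 21% to 56% power for 5 v 5 at the plan's own effect size, and 21% at the only correlation the plan gives.
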